### **B-2.5. Completion of Study Exit Case Report Form**

The **Study Exit Case Report Form** will be completed for every enrolled subject when his/her participation has ceased. (Copy of form included in appendix 1). The form is used to document the final outcome for the subject; the research assistant will indicate the outcome on the form. Possible outcomes include:

- Completed study: Indicating that the subject completed the study visit, defined as having BiliCam images obtained and blood drawn for a TSB level.
- Parent(s) withdrew consent: Indicating that the parent(s) of a subject changed their mind about participating in the study at any point prior to completion
- Subject lost to follow-up: Indicating that the subject did not return for the study visit and no explanation was provided by the parent(s).
- Excluded by site principal investigator: Indicating that the site principal investigator excluded the subject prior to study completion because of medical complications or other reasons
- Excluded – Use of phototherapy: Indicating that the subject received phototherapy prior to the study visit.
- Other: Other outcome not listed.

Research staff will document on the **Site Enrollment Log** when the **Study Exit Case Report Form** had been completed on each subject by recording the date of completion in the appropriate box on the log for the corresponding study ID number.

### **B-2.6 Data management plan**

The data coordinating center will be at the University of Washington. At each monitoring visit (except the site initiation visit and study closeout) photocopies of the following study forms will be made, and the photocopies provided to the data coordinating center by the study monitor: **Subject Enrollment Case Report Form, Study Visit Case Report Form, and Study Exit Case Report Form**. Photocopies will be made on all subjects with data recorded since the previous monitoring visit for each of these forms. The forms will be hand carried or sent by express mail service to the data coordinating center.

At the data coordinating center, data from the forms will be entered into Excel spreadsheets; there will be one spreadsheet for each form (i.e. 3 total). The coding keys for each spreadsheet are included in appendix 6.

Key variables for the study include the race and ethnicity of participants. Coding of race and ethnicity will be based on guidance provided by FDA. Specifically, for parents who check “other” for race (as recorded on the **Subject Enrollment Case Report Form**) and provide a racial group for this response (e.g. “Haitian”), race data will be recoded based on the guidance provided by FDA and additional guidance as provided in appendix 6.

The following conventions will be used for coding race and ethnicity.

- Each major race group (American Indian/Alaska Native, Asian, African American/ Black, Pacific Islander/ Hawaiian Native, White, Other) will be coded as either “0” indicating not checked, or “1” indicating checked.
- If only “other” is checked and the only race specified is “Hispanic,” “Latino” or other group that are designated as “Hispanic/Latino” ethnicity, all racial groups will be coded as 0 and the ethnicity will be coded as “1” indicative of Hispanic/Latino ethnicity.
- If at least one racial group is checked on the **Subject Enrollment Case Report Form**, and no box is checked for Hispanic/Latino ethnicity, ethnicity will be coded as “0”, indicative of non-Hispanic/Latino ethnicity.
- If no race group is checked and no Hispanic/Latino ethnicity box is checked, all race and ethnicity groups will be coded as “9” indicating missing.

All data will be double entered onto separate excel spreadsheets; each spreadsheet will be printed and signed by the staff at the data coordinating center who entered the data. The spreadsheets will be imported into files on the Stata statistical software program (StataCorp LP, College Station, TX). The accuracy of data entry will be assessed by comparing double-entered databases in Stata (i.e. the value for each variable in entry 1 will be subtracted from the value in entry 2, results will equal 0). Any discrepancies will be resolved by reviewing the data as recorded on the photo copied CRF. If data on the photo copied study form are illegible or unclear, the research staff at the site will be contacted and the source document reviewed.

Once reconciled, data from the **Subject Enrollment Case Report Form** and **Study Visit Case Report Form** databases, will be merged. The age in hours of each subject when BiliCam data were obtained and when the blood was for TSB measurement was drawn will be calculated by subtracting the date and time of the respective event from the date and time of birth, and these ages in hours will be included in the data provided to the project biostatistician. To validate and clean the data, the age in hours for the BiliCam test and blood draw for TSB measurement will be checked for out range values (i.e. < 0 hours or > 192 hours); a similar process will be done to identify BCB values out of range (> 20 mg/dL). For identified cases, CRFs and source documents will be reviewed and the spreadsheet corrected using the **Data Clarification Form** as needed. Each spreadsheet will be “locked down” at the data coordinating center, printed out and signed. Spreadsheets including data from merged **Subject Enrollment Case Report Form** and **Study Visit Case Report Form** of subjects who have completed the study will be provided to the project biostatistician on a recurring basis (as described in section B-2.7). These spreadsheets will sent electronically from the data coordinating center, with de-identified data only, on study subjects; no PHI or other identifying information will be included. Prior to providing the spreadsheets, date and time of birth, date and time of collection of BiliCam images and BCB results, and date and time of blood draw for the TSB measurement will be deleted.

At the conclusion of the study, or as needed, the data coordinating center will send the spreadsheet containing data from the **Study Exit Case Report Forms** of study participants and the spreadsheet containing de-identified data from the merged **Subject Enrollment Case Report Forms** and the **Study Visit Case Report Forms** to the sponsor. The sponsor will lock down the spreadsheet; no changes will be allowed. Final copies of each of the spreadsheets will all the data included will be maintained at the data coordinating center.

Copies of completed **Adverse Event Case Report Form, BiliCam Incident Report Forms** and **Protocol Deviation and Other Problems Report Forms** will be checked by the study monitor to ensure they do not contain PHI, collated, and provided to the sponsor.

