#### B -2.3.2. Completing the Study Visit Case Report Form

After obtaining the BCB result on the mobile phone assigned to the study, the research assistant will record the value, and the date and time that the images were obtained, on the **Study Visit Case Report Form**. If a BCB value was not obtained, the research assistant will record "N/A" for the result, and indicate the reason why the BCB value was not available. Possible reasons for not obtaining a BCB value include not obtaining all needed images, issues with lighting, no value downloaded to phone after images are submitted to the server, or a value reported as ">20.0," i.e. outside of measuring range of the device. The initials of the research staff who performed the BiliCam test will be recorded on the CRF.

The calibration card used for the BiliCam test will be affixed to page 2 of the **Study Visit Case Report Form** in the spot indicated on the form.

At the time that the "study" TSB level result is available from the clinical laboratory at each site on a study subject, the level (in mg/dL) will be recorded on the **Study Visit Case Report Form**. In addition, the date and time that the blood was reported as being obtained will also be recorded on the CRF. For subjects in whom the "study" TSB level is a value that was obtained for clinical purposes (including all subjects from Simultaneous enrollment plan sites and a portion of subjects at sites using the Staged enrollment plan), if more than one valid level was obtained within 2 hours of the time that the BiliCam images are obtained, the TSB level drawn closest to the time that the BiliCam images were obtained will be selected as the "study" value. On the **Study Visit Case Report Form** the research assistant will indicate whether the listed TSB value was obtained specifically for the study or for clinical purposes. If no valid TSB level is available, the research assistant will record "N/A" for the result and indicate the reason on the form. Possible reasons include a blood sample that was too hemolyzed for analysis, an inadequate sample (i.e. quantity of blood not sufficient for the assay), and parents declining a study blood draw.

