When paired TSB and BCB data are available for 50 participants and again for 125 participants, interim analyses will be conducted for futility assessment only. There will be no interim superiority analysis and the study will not be terminated early due to favorable results. Therefore, no potential false positive error will be incurred. For each futility analysis, a locked down data spreadsheet will be provided by the data coordinating center to the project biostatistician for Pearson's correlation coefficient assessment. If the hypothesis used to power the study, i.e. an underlying true correlation coefficient of 0.90, is rejected at a 1-sided  $p < 0.0025$  level, early study termination will be suggested to the sponsor for consideration. If a true 0.90 correlation is rejected at a 1-sided  $p < 0.00025$  level, early termination will be strongly recommended to the sponsor. The project biostatistician's communication to the sponsor will consist of one of the following three recommendations regarding the study conduct: (a) continue as planned, (b) early termination might be considered, (c) early termination is strongly recommended. When data collection has been completed at all study sites, the project biostatistician will receive a locked down data spreadsheet with all study data and will conduct the final analysis as described above. The project biostatistician will provide a report to the sponsor on the results of the analysis.

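### Does the as-needed release of the merged BCB-TSB spreadsheet to the sponsor undermine the limit on interim communication?

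*Combined protocol and SAP*

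**What the plan says.** Section B-2.6 sets the timing of the sponsor's data: "At the conclusion of the study, or as needed, the data coordinating center will send the spreadsheet" of exit data and the de-identified merged file of the Subject Enrollment and Study Visit forms. It names no trigger or approver for a transfer before study end.

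The Study Visit form carries both measurements (section B-2.3.2). For BCB: "After obtaining the BCB result on the mobile phone assigned to the study, the research assistant will record the value". For TSB, once the "level result is available from the clinical laboratory at each site on a study subject, the level (in mg/dL) will be recorded".

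The spreadsheets sent to the biostatistician are "with de-identified data only, on study subjects; no PHI or other identifying information will be included", and B-2.6 also deletes dates and times from them. The paired values must remain, because r is computed from them.

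For each futility look, at 50 and 125 pairs, section B-2.7 says that "a locked down data spreadsheet will be provided by the data coordinating center to the project biostatistician". The biostatistician's "communication to the sponsor will consist of one of the following three recommendations regarding the study conduct": continue, consider stopping, or stop strongly recommended. At the milder boundary, "early study termination will be suggested to the sponsor for consideration". A results report follows only once data collection is complete.

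**The concern.** A closed list of three messages normally exists to keep interim results from the party that makes decisions about the study. If that party can receive the underlying pairs at any time, the list does little. De-identification protects privacy but does not hide r.

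Three decisions stay open while data accrue: whether to act on a futility recommendation (B-2.7), whether to modify the app (B-2.3.4, D-3.0), and whether to use more than three sites (B-2.0, which does not say who decides). Any of them could be made with knowledge of the running correlation. In a study meant to support comparability with a predicate device, that would be a question of trial integrity even if every stated figure were right.

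**Working it through.** **Inputs.** Goal 0.83, assumed true r 0.90, two-sided 95% CI and 200 evaluable pairs (B-2.7.1). Looks at 50 and 125 pairs, with one-sided boundaries p < 0.0025 and p < 0.00025 against r = 0.90 (B-2.7). The method is Fisher's z with standard error 1/sqrt(n − 3), assuming bivariate normal data.

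**Step 1: the plan's own figure.** Power = Φ[(atanh 0.90 − atanh 0.83) × sqrt(197) − 1.96] = Φ[(1.4722 − 1.1881) × 14.036 − 1.96] = Φ(2.03) = 97.9%. This agrees with the stated figure of more than 95%. Simulation gives 98.0%.

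**Step 2: what the message reveals.**
- Passing at 200 needs r ≥ tanh(1.1881 + 1.96/14.036) = 0.869.
- Stopping might be considered when r falls below tanh(1.4722 − 2.807/sqrt(n − 3)): 0.787 at n = 50 and 0.839 at n = 125.
- Stopping is strongly recommended below 0.746 and 0.820 respectively.

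At 125 pairs, the message to continue therefore covers every observed r from about 0.839 upward.

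**Step 3: how much more the file would show.** Chance of passing at 200, given r at 125 pairs (simulation of the remaining 75 pairs, same TSB spread):

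| r at 125 | true r 0.83 | true r = observed | true r 0.90 |
|---|---|---|---|
| 0.84 | 0.4% | 0.7% | 26% |
| 0.86 | 5% | 22% | 75% |
| 0.88 | 28% | 87% | 98% |
| 0.90 | 67% | >99% | >99% |

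The file is clearly more informative than the message. Under the plan's own assumption, though, the low rows are rare. If true r is 0.90, the chance of seeing 0.84 or less at 125 pairs is Φ[(atanh 0.84 − atanh 0.90) × sqrt(122)] = Φ(−2.77), about 0.3%. For 0.86 or less it is about 2.4%. If true r is lower than 0.90, they are not rare.

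**Step 4: whether that knowledge can change the error rate.** Under B-2.7 a pass can be declared only at the end. At true r = 0.83 the false-positive rate is then 2.5% nominal (2.6% simulated). It would rise to about 6.2% if success could be declared at 50, 125 or 200 pairs, but B-2.7 rules that out.

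**Step 5: the open decisions.**
- *Futility.* Stopping for poor results can only remove passes.
- *Sites.* Enrollment ends at 225 completers (C-2.0), with at most 75 completers per site (B-2.1). Extra sites cannot extend the sample.
- *App.* The algorithm is locked (B-1.1). No change affecting clinical function is anticipated, and any change must be accounted for in the analysis (B-2.3.4). D-3.0 confines updates to those needed for the study to continue and has them documented. The software version is recorded with each sample (D-4.0).

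**Step 6: whether the plan masks the sponsor.** No section says so. E-2.0 opens source documents to sponsor audit at any point from study start. B-2.8 requires all case report forms to be monitored, and section E has a monitor from a CRO chosen by the sponsor photocopy and collect them. Each Study Visit form shows the pair.

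**The case for a change.** The strongest case for a change is that it is cheap. If only a final transfer was meant, dropping the as-needed option for the merged file costs a few words and alters no sample size, criterion or interim rule. The later statement that the sponsor locks the file does not settle the timing, because interim spreadsheets are also described as locked. A compiled file is also far easier to use than individual forms seen at audit.

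Much of this stands. The clause is loose, it sits awkwardly beside B-2.7, and a mid-study transfer would disclose r. One lever is not fully closed either: the mix of sites could alter the TSB spread and hence r, and nothing requires that choice to be made without sight of the pairs.

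The inference that the limit would be bypassed does not stand. The three-message limit binds only the biostatistician, and B-2.7 gives no purpose for it. Rewording B-2.6, even with a matching sentence on app changes in B-2.3.4, would leave the audit and monitoring routes open and suggest a barrier that the protocol does not have. Holding the pairs back could also delay the iPhone 7 algorithm work described in section A, if that work needs TSB values before final lock.

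**Conclusion.** No change is needed. The as-needed clause is an undefined term in a data-transfer paragraph. It does not contradict the analysis plan, and ordinary data management can settle when a transfer is made. Followed as written, the plan gives a sound primary result: power 97.9% at true r = 0.90 and one-sided error 2.5% at r = 0.83. No stated figure is wrong, and the documents give no basis for sizing a bias.

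This rests on three assumptions: the bar on favorable stopping is kept, all evaluable pairs are analysed against the fixed criterion, and any app change is documented and accounted for as promised. The documents do not show that an early transfer was planned. The conclusion would differ if they stated that the sponsor is masked, because the as-needed clause and the audit and monitoring access would then conflict with that statement.

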## **B-2.7 Analysis plan**

For all enrolled subjects, a descriptive summary will be provided for gender, race, ethnicity, age (hours) at the time that blood was drawn for the TSB, age at the time BiliCam images were taken, and TSB and BCB values. The same summary will also be provided for all evaluable subjects, i.e. subjects with paired TSB and BCB values. Continuous measures will be summarized as mean, standard deviation, median, minimum and maximum. Categorical variables will be summarized as frequency and percentage for each category.

The correlation coefficient (Pearson's  $r$ ) and 95% CI will be calculated for paired TSB and BCB values for all evaluable subjects. This is the primary study outcome. Secondly, the slope and the intercept (with 95% CIs) for the BCB vs. TSB regression line will also be calculated. Correlations between BCB and TSB among participants from different racial and ethnic groups will also be presented. A Bland-Altman analysis will be performed to characterize differences between paired TSB-BCB values; the mean bias and limits of agreement will be calculated.

When paired TSB and BCB data are available for 50 participants and again for 125 participants, interim analyses will be conducted for futility assessment only. There will be no interim superiority analysis and the study will not be terminated early due to favorable results. Therefore, no potential false positive error will be incurred. For each futility analysis, a locked down data spreadsheet will be provided by the data coordinating center to the project biostatistician for Pearson's correlation coefficient assessment. If the hypothesis used to power the study, i.e. an underlying true correlation coefficient of 0.90, is rejected at a 1-sided  $p < 0.0025$  level, early study termination will be suggested to the sponsor for consideration. If a true 0.90 correlation is rejected at a 1-sided  $p < 0.00025$  level, early termination will be strongly recommended to the sponsor. The project biostatistician's communication to the sponsor will consist of one of the following three recommendations regarding the study conduct: (a) continue as planned, (b) early termination might be considered, (c) early termination is strongly recommended. When data collection has been completed at all study sites, the project biostatistician will receive a locked down data spreadsheet with all study data and will conduct the final analysis as described above. The project biostatistician will provide a report to the sponsor on the results of the analysis.

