## **B-2.2. Enrollment plan**

The goal of the enrollment plan is to obtain data on newborns across the entire measuring range of BiliCam (0-20 mg/dL) while oversampling newborns with high TSB levels. The use of two enrollment plans will enable this distribution. At sites using the Simultaneous enrollment plan, newborns will be enrolled at the time (within 2 hours) that blood is being obtained for a TSB level because the newborn is clinically jaundiced (i.e. the TSB is being ordered for clinical purposes). Thus, enrollment and the study visit will occur simultaneously. At Staged enrollment plan sites, subjects will be enrolled prior to being 48 hours old; these subjects will have a study visit after they are 48 hours old (i.e. the enrollment and the study visit will occur at different times). For these subjects, blood will be obtained for a TSB level as part of the study at the study visit.

A subject will be considered to be enrolled in the study once the consent is signed by his/her parent. Once enrolled, a subject's participation will be documented on the study case report forms and the subject will be included in the analyses of study data.

Enrollment procedures are described in detail below.

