### **B-2.7.1. Acceptance criteria and sample size considerations**

In studies supporting FDA 510(k) applications for the predicate device (JM-103), correlation coefficients ranged from 0.84 – 0.946. Based on these studies, the acceptance criterion for demonstrating that BiliCam has comparable accuracy as the predicate device is: the lower limit of the 2-sided 95% CI around the point estimate for the correlation coefficient for the entire group of evaluable subjects will be  $\geq 0.83$ .

It is planned to continue enrollment until 225 subjects (75 at each site) complete all study procedures (as defined in section B-2.1). It is possible that data on BCB and/or TSB measurements may not be available on a limited number of subjects who complete the study because of a laboratory issue with the TSB (e.g. specimen too hemolyzed for assay) or because of problem with the BCB value (e.g. out of range). The sample size of 225 enrolled subjects will ensure that paired BCB-TSB levels will be available on a minimum of 200 evaluable subjects for the primary analysis (correlation between paired BCB-TSB levels). Based on previous studies of BiliCam, it is estimated that the underlying true population correlation between BCB and TSB measurements is  $\geq 0.90$ . With a sample size of 200 evaluable subjects, the chance for the lower limit of the 95% CI for the

observed correlation to be  $\geq 0.83$  is higher than 95%.

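### Accuracy by race or ethnicity is to be reported only as Pearson's r, which cannot show a constant over- or under-reading in one group

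*Combined protocol and SAP*

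**What the plan says.** Section B-2.7 plans four accuracy analyses:

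- Pearson's r with its 95% CI in all evaluable subjects (the primary outcome).
- The slope and intercept of a single BCB-on-TSB regression line.
- The one analysis tied to race or ethnicity: "Correlations between BCB and TSB among participants from different racial and ethnic groups will also be presented".
- An agreement analysis, for which no group is named: "A Bland-Altman analysis will be performed to characterize differences between paired TSB-BCB values; the mean bias and limits of agreement will be calculated".

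The descriptive summary, which includes TSB and BCB values, covers all enrolled subjects, and then: "The same summary will also be provided for all evaluable subjects, i.e. subjects with paired TSB and BCB values". Section B-2.7.1 requires a lower 95% confidence limit of at least 0.83 around "the point estimate for the correlation coefficient for the entire group of evaluable subjects".

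Section B-2.6 states: "Key variables for the study include the race and ethnicity of participants". On coding, "Each major race group (American Indian/Alaska Native, Asian, African American/ Black, Pacific Islander/ Hawaiian Native, White, Other) will be coded as either" 0 or 1, so one infant can belong to several race groups. Where the only race entry is a Hispanic or Latino term, "all racial groups will be coded as 0 and the ethnicity will be coded as" 1. Sections D-5.0 and D-6.0 describe a device that predicts serum bilirubin irrespective of race.

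**The concern.** Pearson's r measures how tightly points follow a straight line, not whether the device's values equal the reference values. If the device reads 2 mg/dL high in every infant of one group, that group's r is the same as with no error at all. Group r does still inform on random error within the group.

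The device works from measured skin colour (section B-1.0), so an offset that varies with pigmentation is a natural thing to look for. Section B-1.1 shows how a table of group correlations tends to be read. Its statement that the device performed well across skin tones rests on group values of r (0.88 to 0.92), while its bias of 0.01 mg/dL is given in the text only for all 530 infants together. If this trial reports the same table, a constant shift in one group would not appear in it and would be diluted in the pooled bias. What is at stake is the secondary evidence on performance across groups.

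**Working it through.** **Inputs.** True r = 0.90, n = 200 and the 0.83 limit are from B-2.7 and B-2.7.1. The SD of BCB − TSB, 1.8 mg/dL, is from B-1.1. The size of the affected group is an assumption: 41 of 200, close to the 110/530 share of African American/Black infants in B-1.1, because this trial sets no group mix. The shifts are illustrative; the documents give none, and no threshold for an important one.

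**1. The plan's own power figure.** Φ[(atanh 0.90 − atanh 0.83)·√197 − 1.96] = Φ(2.03) = 97.9%. This agrees with the stated figure of more than 95%.

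**2. Invariance.** corr(TSB, BCB + c) = corr(TSB, BCB) for any constant c. In a simulated group of 42, r was 0.904174 at shifts of 0, −1, −2 and −3 mg/dL, while the mean difference moved by exactly the shift.

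**3. Dilution in the pooled Bland-Altman analysis.** With group share p = 41/200 = 0.205 and shift d = 2:

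- Pooled bias = p·d = 0.205 × 2 = 0.41 mg/dL.
- Pooled SD of differences = √(1.8² + 0.205 × 0.795 × 2²) = 1.97.
- Half-width of the pooled limits = 1.96 × 1.97 = 3.87, against 1.96 × 1.8 = 3.53 with no shift.

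**4. Chance that the primary criterion is still met.** With equal SDs for BCB and TSB, SD² = 1.8²/(2 × 0.10) = 16.2, and pooled r = 0.90·√[16.2/(16.2 + p(1−p)d²)]. This gives 0.896, 0.882 and 0.862 at d = 1, 2 and 3. The formula in step 1 then gives about 96%, 80% and 35%.

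Simulation (40,000 trials per scenario, Fisher-z lower limit ≥ 0.83) used three ways of splitting the error, each with r = 0.90 within groups and the same TSB distribution in each group:

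| Shift (mg/dL) | BCB = TSB + error | Equal SDs | TSB = BCB + error |
|---|---|---|---|
| 0 | 98% | 98% | 98% |
| 1 | 96% | 96% | 95% |
| 1.5 | 92% | 91% | 89% |
| 2 | 82% | 80% | 75% |
| 3 | 39% | 35% | 24% |

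Section B-2.2 plans enrollment "while oversampling newborns with high TSB levels", so group means may differ. Letting the affected group's mean lie from 2 mg/dL below to 2 mg/dL above the rest widens the ranges to 95–99% at shift 1, 75–96.5% at 2 and 22–82% at 3. Holding the overall TSB SD at 3.72 as well (BCB = TSB + error) gives 93–98%, 64–94% and 14–75%; in that variant r within groups falls to about 0.896 at the extremes. Shifts here are upward. A downward shift mirrors them, with the sign of the mean difference reversed.

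**5. What group bias estimates would deliver.** The 95% CI half-width for a group's mean bias is t(0.975, n−1) × 1.8/√n. For each limit of agreement it is t × 1.8 × √[1/n + 1.96²/(2(n−1))].

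| n in group | Mean bias (± mg/dL) | Each limit (± mg/dL) |
|---|---|---|
| 41 | 0.57 | 0.98 |
| 20 | 0.84 | 1.46 |
| 10 | 1.29 | 2.28 |

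**The case against.** The strongest reply is that B-2.7 does not forbid a Bland-Altman analysis by group. That sentence follows directly on the group-correlation sentence and names no population. The data will exist, the rows could be added at reporting, and no hypothesis or criterion hangs on the group correlations. This is correct as far as it goes. But pooled is the natural reading, and a group analysis chosen after the results are seen is weaker than one committed to now.

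A second objection is that the pass probabilities concern a pooled criterion that nobody offers as a test of group bias, and that they rest on assumed shifts. This stands in part. They show only that the primary result is not a dependable safeguard; the defect itself follows from the invariance of r and needs no assumption.

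A third is that a raw mean difference depends on TSB level when the BCB-on-TSB slope is below 1. With slopes of 0.90 and 0.81, as in the second and third models, a group whose TSB averages 2 mg/dL higher would show (0.90 − 1) × 2 = −0.2 to (0.81 − 1) × 2 ≈ −0.4 mg/dL with no group effect. This is a fair caution for interpretation. It does not defeat a descriptive estimate, and showing each group's TSB level, or its slope and intercept, would help.

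Finally, the figures in B-1.1 could not be seen, so the remark that its bias is pooled applies to the text only.

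**Conclusion.** The concern holds. The only accuracy statistic that the plan ties to race or ethnicity cannot detect a constant offset in a group, at any sample size. The pooled analyses dilute such an offset and would not identify the group. Under the assumptions stated, with equal TSB distributions, a 1 mg/dL shift in about a fifth of infants leaves the criterion met 95–96% of the time and a 2 mg/dL shift 75–82%. Only at 3 mg/dL is it more often failed than met (24–39% pass), and even that depends on group TSB means.

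Nothing in the documents shows that a shift exists. The primary conclusion on overall r and the stated power are not in dispute. The plan should be changed on this point because its secondary evidence cannot support a statement that accuracy is the same across racial groups.

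**What to change.** Add one sentence to B-2.7: *Mean bias (with 95% CI) and limits of agreement will also be presented, with n, for each racial and ethnic group.* Define bias as BCB minus TSB and use a t-based interval. Report one group at a time, because the coding in B-2.6 lets groups overlap. Label the estimates descriptive, without multiplicity adjustment, and base any statement about performance across groups on them as well as on r.

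Two additions are optional. The first is each group's mean TSB, or its slope and intercept, to help read level-dependent differences. The second is a contrast of members with non-members of a group. If it is used, infants with no reported race (Hispanic-only responses coded 0 on every race, or code 9) should be left out of the race contrasts or shown separately, not counted as non-members.

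The cost is a few table rows, with no new data and no change in sample size. Small groups will be imprecise, as the half-widths above show, and infants with no reported race contribute to no race row.
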